A single informed consent form (see Appendix A. Informed Consent Form) will cover all phases of the study (clinical intake, pre-intervention assessment, intervention, and post-intervention assessment). Prior to the clinical intake, a copy of the Informed Consent Form will be emailed to participants. At the start of the clinical intake, a trained research staff member will give each parent an overview of the study in its entirety and review confidentiality practices, potential risks, and any benefits. Participants will also be informed that as this is an intervention development project, the intervention group coleaders are involved in the research and will have access to assessment data. Limits to confidentiality will be covered (as in the case of abuse of vulnerable populations, harm to self or others), as will the steps that will be taken if this information is revealed. Because the clinical intake and the assessments will specifically ask about suicidality, parents will be told in detail what procedures will occur if they are judged to be a risk to themselves or others (see Appendix X. Critical Risk Protocol). Parents will be invited to ask questions and will then provide consent via electronic signature on the Informed Consent Form and email it back to the staff member conducting the clinical intake.

At the start of the post-intervention qualitative interview, the trained research staff member conducting the interview will briefly cover the purpose of the exit interview and review the relevant portion of the consent form with the parent. Parents will be asked to verbally reaffirm their consent to participate. We will clearly track that the parent's consent to participate in the study was collected at the clinical intake and at the post-intervention exit interview (see Appendix Z. Documentation of Informed Consent).

A copy of the informed consent form will be posted on a Federal website (e.g. clinicaltrials.gov) after the study is closed to recruitment and no later than 60 days after the last study visit by any subject.

Research roles for consent procedures. All research staff members involved in collecting informed consent will be highly trained. Specifically, through the first two years of a clinical graduate student's studies, they take courses on assessment procedures, psychopathology and development, and begin working as individual and group therapists in the local psychology clinic under a licensed psychologist's supervision. This training includes exposure to a clinical population directly, and specialized training in assessing risk.

F. Provisions for Participant Privacy and Data Confidentiality

Methods of data collection from participating parents will occur through UO Qualtrics and a HIPAA compliant version of Zoom. Zoom will be used for clinical intakes, the intervention sessions and the final exit interview. OneDrive will be the primary cloud storage method for identifiable or highly sensitive data. OneDrive includes security controls and encryption of data that satisfy the requirements of the HIPAA Security Rule (https://www.hipaajournal.com/onedrive-hipaa-compliant/).

Upon entering the study, the parent will be assigned a unique, random ID number, which will be used to label each parent's data throughout the study phases (i.e. intake, pre-intervention assessment, intervention, post-intervention assessment). Participants will be explicitly directed not to provide any identifying information, including their name or their child's name when completing Qualtrics questionnaires, and instead will be directed to provide only their unique ID number. A master list linking the ID number to identifiable information (i.e. parent and child's real names, contact information) will be stored separately from all other data, on a password-protected server, only to be accessed by key study personnel.

Questionnaire data will be collected via the Qualtrics system and will be accessible on the Qualtrics website. Qualtrics assigns a random code to each participant. Once the data are downloaded, the Qualtrics codes will be replaced with the family's unique ID number. Data will be downloaded

temporarily and moved to be stored on OneDrive, accessible only by the research team. Copies of the data will be immediately deleted from local computers after being added to OneDrive.

Video recordings from the clinical intake, intervention sessions and final exit interview will initially be stored on secure servers of the University of Oregon and later transferred to secure, online cloud storage (OneDrive) with extra security features to encrypt and protect the data. All video recordings will be accessible only by the research team. Video recordings will be labeled with a random code number and not participant's names or other identifying information. Video recordings will be stored on OneDrive for 3 years after publication of the data, at which time they will be destroyed. Video recordings of the clinical intake and intervention sessions may be used for the purpose of internal review when consultation about a diagnosis or treatment is needed, to enhance therapist skill, further refine the development of the intervention, and train other future therapists. Research assistants will be trained to qualitatively code the exit interviews. All research assistants will complete human subjects training and will therefore be bound to confidentiality rules.

Clinical records which are a standard part of maintaining a client file such as session notes, emergency contacts, and release of information forms (see Appendix Y. Release of Information Authorization Form) are not considered study data and will also be stored on OneDrive, but kept separate from study data. No person who is not part of the research team will have access to this identifiable data.

Emails to enrolled participants (e.g. Zoom links, Qualtrics questionnaire links) will be sent via an encrypted email service (Hushmail). Phone communication with the research team may be conducted using Google Voice. Text messages sent to participants will not include identifying participant information unless first volunteered by the individual (e.g. a first name). Participant names will not be saved in a contact list connected to the Google Voice account. Their unique phone number will be used to search for the message thread. All messages will be permanently deleted from the device upon fulfillment of the intended purpose.

Sharing data. This research study is part of a larger set of related studies being conducted by the Center on Parenting and Opioids (CPO), a National Center co-located at UO's Prevention Science Institute (PSI), UO's Center for Translational Neuroscience (CTN) and Oregon Health and Sciences University (OHSU). The research at CPO is funded by an award from the National Institute on Drug Abuse (NIDA). De-identified data collected as part of the current study will be shared to the CPO Data Repository (CPO-DR). This repository stores data from many CPO-affiliated studies and is maintained by CPO staff. This expectation for data sharing is in accordance with guidelines from national funding agencies (e.g., see NIH Data Sharing Policy here:

http://grants.nih.gov/grants/policy/data_sharing/index.htm).

We will not share any personally identifiable information about the participants in our study to the CPO-DR. We will securely transfer data as in accordance with CPO policies and procedures. The CPO-DR is designed to store encrypted, password-protected data behind firewalls. Data in the CPO-DR will be preserved indefinitely. Because we will not share identified data to the CPO-DR, data from participants in our study cannot be directly linked to data collected by other CPO research. In other words, no CPO researchers will be able to know if someone who participated in our study also participated in another CPO-affiliated study. Instead, data from our study may be combined with data from other CPO studies. Many of the studies that are part of the CPO have agreed to administer the same set of questionnaires, so that we can combine the responses across multiple studies. Increasing the sample size in this manner will make us more licensed to generalize the findings. Other researchers outside of the research team and the CPO research teams can request access to the data in CPO-DR. Only researchers who have agreed to protect the confidentiality of participants and the privacy of the data will be authorized to access the CPO-DR. CPO staff will be responsible for determining which researchers have access to the data. It is possible that data in the CPO-DR could be accidentally shared with an unauthorized person who may attempt to learn participants' identities. We will not share any personally identifiable information from our study to the CPO-DR. So, the risk is small of someone learning the identity of any of our study's participants by accessing CPO-DR data.

We will ask participants to consent to sharing their de-identified data to the CPO-DR in the Informed Consent Form (see Appendix A. Informed Consent Form). Participants who prefer not to share their de-identified data to the CPO-DR may opt not to participate in the study.

Certificate of Confidentiality. To help us protect the privacy of participants, a Certificate of Confidentiality (CoC) from the National Institutes of Health (NIH) was automatically issued as part of the CPO's NIDA P50 grant. This CoC will cover the current research. The research team can use the CoC to legally refuse to disclose information that may identify participants in any federal, state, or local civil, criminal, administrative, legislative, or other proceedings (e.g., if there is a court subpoena). The researchers would use the Certificate to resist any demands for information that would identify participants. The Certificate of Confidentiality would not be used to prevent disclosure to state or local authorities of child abuse and neglect, or harm to self or others. It will also not be used to prevent an audit by the UO IRB or federal funders.

G. Potential Research Risks or Discomforts to Participants

Clinical intake risks. While the clinical intake will invite parents to share potentially painful life events, the intake will be similar to what would be experienced in any clinical or psychological treatment setting. There could be a risk in that parents may meet criteria for mental disorders, which could be upsetting to them. Additionally, if the parent is actively suicidal, the intake clinician will conduct a suicide risk assessment using the Linehan Risk Assessment and Management Protocol (See Appendix W. LRAMP). Following the diagnostic interview, the intake clinician will inform parents about any diagnoses made and will provide referrals upon request. If the parent IQ scores are lower than 70 on the PPVT-IV (i.e. the parent is ineligible), the intake clinician will provide the parent with the results and the intake will be ended prior to completion of the SCID-5 (see Appendix AA. Clinical Intake Debriefing Script). Intake clinicians are well-trained and supervised (by [name]) research staff members with experience in assessment and provision of clinical feedback to individuals from clinical populations. Intake clinicians will also provide referrals if needed and participants will be provided the PI's contact information should they have additional questions about their experience during intake. Parents will be informed of the risk of experiencing upsetting emotions during the informed consent process.

Assessment risks. Answering questionnaires about their mental health, their child's behavior and their own parenting may bring up negative emotions, but the level of distress expected is minimal. Parents will be informed of these risks during the informed consent process and reminded that their participation is voluntary.

DBT Skills +PT intervention risks. Parents in the DBT Skills +PT group will potentially encounter risks by virtue of being in a weekly intervention. By applying DBT and parenting skills in their everyday lives, and by being asked to share about these experiences, parents may experience painful emotions. However, it is our estimation that the negative emotions experienced would be similar to parents engaging in other forms of psychological treatments and in fact, is likely to be very beneficial. Risks of psychotherapy are explicitly discussed in the informed consent form.

Telehealth-related risks. There are some specific risks associated with telehealth services. First, although it is HIPAA compliant, it is not possible to completely guarantee the security of the Zoom software. As with any technology, there is a chance of a security breach that would affect participants' privacy of personal and/or medical information. Second, as parents will be completing sessions in their own home, it is not possible to guarantee the same level of privacy as in a clinic. Third, it is possible

that parents' confidentiality may be breached if other members of the therapy group are not in a confidential setting. Fourth, it is more difficult for therapists to respond immediately to an emergency situation, should that occur during a session.

We will mitigate these risks by providing instruction to group members on how best to create a private and secure space for themselves and other group members (e.g. use of a secure internet connection, use of headphones during session, conducting sessions in a private room, instructing participants not to record or photograph sessions). To mitigate the risks of emergency situations, participants will be asked to provide their location at the start of each session and therapists will maintain emergency contacts for each group member. Based on best practices for assessing and treating suicidal individuals via telehealth, Appendix X. Critical Risk Protocol includes guidelines for such cases which will inform our procedures. All telehealth related risks will be covered in the consent form (see Appendix A. Informed Consent Form).

Unimproved or worsening of symptoms. Continued or worsening of symptoms is always a risk, even for those engaged in treatment. While these risks are not specific to the proposed study intervention, it is important for the study team and parents to be aware of the potential adverse events associated with emotion dysregulation and mental disorders.

Confidentiality. The potential for breach of confidentiality exists with the clinical intake, assessment, and DBT +PT intervention digital files and for clinical records. Furthermore, as will be reviewed for all parents at the intake, confidentiality may be broken if child abuse or neglect, or intention to harm self or other is disclosed by the parent. As the intervention will involve parents sharing and discussing different parenting situations, it is possible participants may disclose information regarding child abuse or domestic violence. In such cases, the co-leaders will follow-up with parents to clarify the risk and current safety of their children and determine whether mandated reporting is warranted. The PI and clinical supervisor will report this information to child protection services, a primary health care provider, or emergency services, depending on the specifics of the disclosure. Procedures for responding to such critical incidents are detailed in Appendix X. Critical Risk Protocol.

Data Safety Monitoring Plan. The funding agency required a Data Safety Monitoring Plan for this research (see Appendix CC. Data Safety Monitoring Plan). There was no funder requirement for an established Data and Safety Monitoring Board/Committee (DSMB/C) as noted in the DSMP.

H. Potential Benefits of the Research

Parents who participate in the DBT +PT intervention will receive an evidence-based treatment that has been found effective in treating substance abuse in emotionally dysregulated populations, and which is scarcely available (or not adherently provided) in Eugene (i.e. DBT Skills), as well as evidence-based parent training for children's emotional and behavior problems. They may experience improvements in their mental health and parenting skills, however there may be no direct benefit of participating in the intervention.

Beyond that, participation in this research will contribute to scientific understanding of the effectiveness and feasibility of integrating these treatments. Our study will facilitate future research and the development of new clinical interventions that will ultimately benefit other parents and families.

I. Investigator Experience

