2. Evaluate pre -post and weekly changes in measures of parental emotion regulation, parenting **stress, parenting quality and children's mental health**. Across all parents enrolled in DBT+PT, we will evaluate the rate and pattern of change in these interlinked domains which represent risk factors for relapse and further adverse outcomes. We anticipate pre-post changes (2 time points, approximately 20-22 weeks apart) will be comparable to well-established change scores from the clinical trial literature base for DBT Skills and parent training interventions. Additionally, qualitative data from exit interviews with each parent will be analyzed using thematic analyses of responses to evaluate parents' perceptions of changes in their own mental health, their parenting and their children's behavior over the course of the intervention.

Weekly repeated measures (20 time points) will allow us to model the rate and pattern of change from week to week. As the intervention is divided into 4 modules (see Procedures), change patterns will also be examined between modules. Data will be presented descriptively and we expect changes to unfold in a cascading order, with increased use of skills preceding reductions in parent emotion dysregulation, followed by improvements in parenting quality and subsequent improvements in child behavior.

C. Methods, Materials and Analysis

Setting. Clinical intakes, the weekly group DBT Skills+PT intervention sessions, and exit interviews will all be conducted via a HIPAA compliant teleconference platform (i.e. Zoom). The initial online screener, and pre-post and weekly assessments will be conducted via UO Qualtrics questionnaires.

Study design. This study utilizes a mixed methods case study design with continuous assessment of quantitative measures. Figure 1 presents the study phases, along with what participating parents will complete in each phase, and the estimated time needed to complete each phase.

	time required of participants.	Time Estimate
Study Phase Recruitment	Participant action Parents respond to recruitment	N/A
Reciditment	materials	
↓		
Initial Online Screener	Parent completes:	
	DERS	DERS – 5 minutes
	CAGE-AID	CAGE-AID – 2 minutes
		Total: 7 minutes
•		
Clinical Intake	Parent completes:	Demographica 4 minutes
_	Demographic questionnaire	Demographics – 4 minutes
	PHQ-9	PHQ-9 - 3 minutes
	PPVT-V (Q-Global) SCID 5 diagnostic interview	PPVT-V – 20 minutes SCID 5– 180-300 minutes
		Total: 207-327 minutes
.		

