Aim 1. Determine feasibility, acceptability and implementation. Three types of feasibility will be examined. Feasibility of recruitment will be assessed by examining the number of participants meeting eligibility on the initial online screener and the number of participants meeting eligibility following the clinical intake. Feasibility of measurement tools will be assessed by calculating the average time taken by participants to complete the online Qualtrics questionnaires, and the average percentage of missing data from the online questionnaires. Feasibility of the intervention will be evaluated by calculating the average number of sessions attended by parents.

Acceptability will be examined by averaging the total scores obtained from the Client Satisfaction Questionnaire (CSQ-8). In addition, using qualitative thematic analyses, we will report on data collected during the exit interview, identifying overall themes about the intervention that emerge from parents' comments.

We will examine implementation by calculating the average daily number of DBT and parenting skills parents report using each week on their diary card (averaged across parents) and comparing these to skill use reported in other published research (ex. 7-8 DBT skills per week; Gamache [name] et al., 2017). We will primarily report data for Aim 1 at an aggregated group level. We may also include de-identified information at the individual level in the form of quotes from parents' exit interviews.

Aim 2. Evaluate pre-post and weekly changes. We will examine pre-post changes for the primary outcomes of DBT Skill use (DBT-WCCL), parental emotion dysregulation (DERS), parenting stress (PSI) and parenting quality (PS, CCNES). Pre-post change scores will also be calculated for the secondary outcomes of child internalizing and externalizing behaviors (CBCL), child emotion regulation (ERC), parent mental health symptoms (HAM-A, PHQ-9, ADCS). Pre-post change scores will be compared to the clinical trial literature base for DBT and parent training interventions which often use the same measures and for which expected change scores are established. Additionally, based on post-intervention reports during the SCID 5 diagnostic interview, the percentage of parents reporting sustained recovery (vs relapse) from substance use disorder will be calculated and reported.

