Participants. We intend to recruit and conduct intakes with approximately 18 parents, enroll up to 15 eligible parents in DBT+PT, so as to reach our target of 12 parents who complete at least 4 sessions. This attrition rate is based on our lab's prior experience providing DBT Skills to a parent population. Participating parents will be split into three DBT Skills +PT groups that are run at different times over the course of the year. Recruitment efforts will take place twice over the course of the year to facilitate this.

To participate, parents must be 18+ years of age and reside in Oregon, have at least partial custody of a 3-6 year old child, neither parent nor child may have any known developmental disability, and the parent must be proficient in English, as our laboratory is unable to conduct the clinical intake, assessments, and DBT Skills +PT intervention with non-English speaking participants. Parents must also have internet access to facilitate participating in the remote telehealth DBT Skills +PT intervention. Additionally, eligible parents must endorse elevated emotion dysregulation (a score of >88 on the DERS, equivalent to +.5 SD above a normative score; Ritschel, Tone, Schoemann, & Lim, 2015) and endorse 2 or more items on the CAGE-AID screener for past (past 5 years), but not current (not in the past 12 months), substance use.

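### Aim 2 reads uncontrolled pre-post change in about 12 parents against published change scores, with no interval and no untreated reference, so a half-size effect could often pass for a full one

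*Combined protocol and SAP*

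**What the plan says.** Section C describes the design thus: "This study utilizes a mixed methods case study design with continuous assessment of quantitative measures". There is no comparison group. Section B, Aim 2 states: "Across all parents enrolled in DBT+PT, we will evaluate the rate and pattern of change". Pre-post change rests on "2 time points, approximately 20-22 weeks apart", and Aim 2 anticipates that these changes "will be comparable to well-established change scores from the clinical trial literature base".

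Section C, Analyses, Aim 2 turns this into a procedure: "Pre-post change scores will be compared to the clinical trial literature base for DBT and parent training interventions". It names five primary measures (DBT-WCCL, DERS, PSI, PS, CCNES) and several secondary ones, and says that expected change scores are established. It gives no value, SD, source trial, interval, meaning of comparable, or untreated reference.

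On numbers, Section D plans to "enroll up to 15 eligible parents in DBT+PT" "so as to reach our target of 12 parents who complete at least 4 sessions".

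The opening paragraph of Section C, Analyses says the analyses will evaluate to what extent the intervention was effective. The closing paragraph on Aim 2 says they will report the degree to which it changed symptoms and behaviors.

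**The concern.** A published treated-arm change is the sum of the treatment effect, natural course and retest effects. A single-arm change contains the same parts, so agreement between the two does not show that treatment contributed. DERS carries a further risk: a score above 88 is required for entry and DERS is also a primary outcome, so some regression to the mean may remain. Measuring DERS again at pre-intervention reduces this but need not remove it.

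Without an interval, the reader cannot see how wide a range of true changes fits the data, and a weak result can be described as similar to the literature. Section A gives a reason to care: it says parent training works less well in parents with substance use disorder. A shortfall against the benchmark is therefore plausible, and the comparison should be able to show one. At stake is the description of the intervention's effect in a pilot that precedes a larger randomized trial.

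**Working it through.** **Inputs from the plan.** The target is 12 parents and the maximum enrolled is 15 (Section D, Participants). There are two time points and one arm. The plan states no alpha, power, benchmark, SD or correlation, so there is no precision figure to reproduce. The recruitment figures agree with each other: 12/15 = 0.80, that is 20% attrition, and 12/0.80 = 15.

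**Assumed inputs.** Pre-post correlation r of 0.3 to 0.8; equal SDs before and after; normally distributed changes; benchmark 0.8, true change 0.4 and control-arm change 0.2, all in baseline SD; benchmarks treated as known without error.

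**Step 1, precision in SD of change.** Half-width = t(0.975, n−1)/√n.
- n = 12: 2.201/3.464 = 0.635
- n = 15: 2.145/3.873 = 0.554
- n = 8 (an assumed number of post-assessments): 2.365/2.828 = 0.836

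The n = 8 line is there because the target counts parents with at least 4 of 20 sessions, not parents with a post-intervention assessment. At n = 12, an observed change of 0.8 SD of change would carry 0.16 to 1.44; an observed 0.4 would carry −0.24 to 1.04.

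**Step 2, conversion to baseline SD.** SD of change = √(2(1−r)) baseline SD. The two metrics coincide only at r = 0.5.

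**Step 3, how often the benchmark stays inside the interval.** With benchmark 0.8 and true change 0.4, the gap in SD of change is 0.4/√(2(1−r)). The probability that 0.8 lies in the 95% interval comes from the noncentral t distribution with 11 degrees of freedom. The last column, the probability that the interval contains both 0.8 and 0.2, was simulated.

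| r (assumed) | √(2(1−r)) | Half-width, baseline SD, n = 12 | P(0.8 inside) | P(0.2 and 0.8 both inside) |
|---|---|---|---|---|
| 0.3 | 1.183 | 0.75 | 81% | 74% |
| 0.5 | 1.000 | 0.64 | 76% | 66% |
| 0.7 | 0.775 | 0.49 | 63% | 50% |
| 0.8 | 0.632 | 0.40 | 48% | 33% |

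**Step 4, sensitivity to the benchmark.** In SD of change, the power at n = 12 to rule out the benchmark when the true change is half of it is 12%, 24%, 35%, 48% and 71% for assumed benchmarks of 0.5, 0.8, 1.0, 1.2 and 1.6. The gap between full and half effect is no larger than the half-width while benchmark/2 ≤ 0.635, that is up to a benchmark of about 1.27.

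**Step 5, other influences.** Treatment in groups of about 4, with an assumed intraclass correlation of 0.05 to 0.10, multiplies the variance by 1 + 3 × 0.05 = 1.15 to 1 + 3 × 0.10 = 1.30. The n = 12 half-width becomes 0.635 × √1.15 = 0.68 to 0.635 × √1.30 = 0.72. For DERS, selection above +0.5 SD gives a truncated-normal mean of 1.141 SD. Regression to the mean after the screener is then (1 − retest correlation) × 1.141, or 0.11 to 0.34 SD for assumed retest correlations of 0.9 to 0.7. This is an upper bound for the pre-post change, because the pre score is a second measurement.

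**The case against.** The strongest defence is that this is a descriptive pilot. Aim 2 anticipates comparability and sets no test, margin or success criterion, and Section D, Attrition says the case study design does not require inferential analysis. That stands: a reader might infer a formal verdict of comparability, and the documents contain none. It does not answer the point, because an interval is itself descriptive and the effectiveness wording in Section C goes beyond description.

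Second, the two-point comparison is not the plan's only evidence on change. Tau-U, regressions and hierarchical linear models are planned on up to 20 weekly points, covering DBT-WCCL, DERS and PS among the primary outcomes. The SCID-based recovery percentage and the exit interviews add to this. That also stands, but none of it supplies an untreated reference or interprets the literature comparison.

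Third, a reader might infer that the result would be used to size the larger trial. Section B says only that the pilot completes foundational steps; no passage ties the comparison to a sample size or a go/no-go decision.

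Fourth, it is tempting to say that 12 parents can never separate a full from a weak effect. The documents give neither the benchmark nor the correlation on which that depends. With a large benchmark or a high correlation, separation becomes possible.

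Finally, one might ask for a rule that an interval excluding a historical control value shows change beyond natural course. It would not: that value has its own sampling error and comes from a different population.

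**Conclusion.** The point holds in a conditional form. The stated method compares uncontrolled change with published change scores and supplies neither an interval nor an untreated reference, so resemblance to the literature cannot support the effectiveness wording. At n = 12 the half-width is 0.64 SD of change (0.55 at n = 15). With an assumed benchmark of 0.8 baseline SD, a half-size effect would leave the benchmark inside its interval in about 81% to 48% of studies for correlations of 0.3 to 0.8. The size depends on the assumed benchmark and correlation and on 12 parents giving post-intervention data; fewer would widen the interval. Nothing here says that 12 parents are too few for the feasibility aims. This is a worthwhile improvement to the Aim 2 comparison and leaves the design as it is.

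**What to change.** Before analysis, add a short table to Section C, Analyses, Aim 2. For each primary outcome (DBT-WCCL, DERS, PSI, PS, CCNES), give a published treated-arm change and, where one exists on the same instrument, a control-arm change from a waitlist or usual-care arm. Put all values in one stated metric and say which SD is used.

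Report the observed mean change with a t-based 95% CI and the number of parents contributing, beside both references. Label the comparison exploratory, and do not conclude from it that the change is comparable or that the intervention was effective. Where the interval covers both references, say that the data do not distinguish them. No test against the historical control value is needed, and no extra parents or data.

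The cost is a small literature search and a less favourable statement. Section C, Materials notes that these literatures have often used different measures, so some outcomes may have no same-instrument control-arm value; the table should then say so.
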